Five cognitive summary scores were measured at baseline. Multivariate linear regression models were used to evaluate the cross-sectional association between serum bicarbonate and cognition. *Results:* The mean age (SD) and mean (SD) eGFR were 68 (8.5) years and 71 ml/min/1.73m², respectively. Global cognitive and executive functions were positively associated with serum bicarbonate (Table 1). These findings suggest that low bicarbonate levels may be detrimental to neuronal activity and support the need for an interventional trial examining whether correction of acidosis has a beneficial effect on cognitive function.

b) Bicarbonate administration results in improved vascular endothelial function (FMD) in patients with CKD stage 3b-4.⁴⁹ We performed a pilot, prospective, open label 14-week crossover study examining the effect of treatment of metabolic acidosis (defined by a low serum bicarbonate level of 16-22 mEq/L), with oral sodium bicarbonate therapy (dose 0.5 mEq/kg-lean body weight/day) in 20 patients with CKD stage 3b-4. The primary endpoint was change in FMD between treatment and control conditions. *Results:* The mean (SD) age and eGFR was 58.5 (12.8) years and 25.3 (8.3) ml/min/1.73m², respectively. The mean (SD) bicarbonate level increased after sodium bicarbonate therapy from 19.6 (2.9) mEq/L to 22.4 (3.0) mEq/L. BP control was similar between the two conditions. FMD significantly improved after 6 weeks of sodium bicarbonate therapy compared to control conditions (mean difference in %FMD 1.1% in the treatment arm vs. - 0.70% in the control arm, p=0.027), Figure 2. Bicarbonate therapy was well tolerated and there were no significant adverse events.

c) Feasibility of Aim 2 is demonstrated by our groups experience with cerebrovascular hemodynamics. In a small interventional trial of 8 adults over the age of 50 with baseline blood pressure >120 mmHg, 6 weeks of inspiratory muscle strength training (IMST) improved cerebrovascular reactivity compared to control.

	Δ CVR (Δ MCA _{velocity} / Δ end tidal CO2) from baseline Mean (SE)
IMST (Treatment Group) n=4	0.99 (0.31)
Control Group n=4	-0.14 (0.60)

IV. Research Methods

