Subjects. After obtaining their written informed consent, 50 patients with CKD stage 3b-4 (defined as estimated GFR (eGFR) 15-44 ml/min/1.73m²) with metabolic acidosis (defined as a serum bicarbonate level of 16-22 mEq/L, on 2 separate measurements at least 1 day apart), will serve as subjects. **Relevant biological variables:** Men and women 50-80 years old of all races/ethnicities will be included. Major inclusion/exclusion criteria are presented in the table below (Table 1). Only participants aged 50-80 years are included given the high prevalence of cognitive impairment in this age group. We chose a bicarbonate level of 16-22 mEq/L as this defines metabolic acidosis (<16 mEq/L) are excluded. For additional rationale for inclusion/exclusion criteria, please see the Recruitment and Retention Plan. Patients will undergo screening for eGFR and serum bicarbonate at the Kidney Disease Research Center (KDRC) at the University of Colorado Anschutz Campus. The Chronic Kidney Disease Epidemiology Collaboration (CKD-EPI) prediction equation will be used to calculate eGFR.⁵¹ A race modifier will not be used to correct the eGFR equation (all subjects will be categorized as "other".⁵² Patients will be recruited from nephrology clinics at the University of Colorado where the PI has access to over 4,000 CKD patients. We will also recruit

from our CKD database, which contains over 300 CKD patients willing to participate in trials. The Health Data Compass services will also be used to generate a list of potential participants.

Rigorous Experimental Design. A 12-month **pilot, randomized, placebo-controlled, doubleblinded study** with sodium bicarbonate will be conducted. The study will include 5 phases: screening, run-in, baseline, randomization and follow-up.

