Rationale for sodium bicarbonate dose: A dose of 0.5 mEq/kg-LBW/day has been shown to be safe and effective for treatment of metabolic acidosis in patients with CKD.^{49,53-54} Previous studies using this dose of sodium bicarbonate have not reported significant changes in edema, body weight or BP.^{49,53-55} In our **preliminary data**, sodium bicarbonate administration was not associated with an increase in BP or fluid gain in patients with CKD stage 3b-4.⁴⁹ Additionally, we will dose sodium bicarbonate based on LBW, not actual body weight. The volume of distribution of bicarbonate is approximately that of total body water. Total body water is dependent on lean body mass. Standard equations will be used to determine LBW.⁵⁶

b) Placebo: Subjects randomly assigned to placebo will take the same number of capsules as if they were assigned to receive 0.5 mEq/kg-LBW/day of sodium bicarbonate. Participants will take ½ the daily dose in the morning and the other ½ in the evening. The number of capsules will be rounded to the nearest whole capsule. To reduce pill burden and increase compliance the maximum number of pills per day will be six.

Rationale for placebo: A placebo group is necessary to successfully complete our aims. If a placebo group were not included both the investigators and participants would know that they are receiving sodium bicarbonate, which could influence medical management and perception of side effects in the study.

Dose Titration of Study Drug: If at month 3 the serum bicarbonate level not $\ge 23 \text{ mEq/L}$, we will increase the dose of sodium bicarbonate to 0.8 mEq/kg/LBW. This dose was recently used in a randomized trial comparing the safety and efficacy of doses of sodium bicarbonate therapy and was found to be well tolerated without any significant differences in adverse events or hospitalization compared with placebo.⁵⁷

5. Rationale for study duration. Changes in cognitive function, cerebrovascular reactivity and pulsatility can be seen within 4-6 weeks in adults 50 years and older but may require longer periods of time and published data use a period of 3 months to 1 year.⁵⁷⁻⁶¹ Hence, we are proposing a 12-month intervention.

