• **Expected adverse events:** Sodium bicarbonate therapy may cause bloating, flatulence and abdominal discomfort. Although previous studies using similar doses of sodium bicarbonate have not reported significant changes in edema, body weight or BP,^{49,53-55} sodium bicarbonate may cause edema to develop or worsen thereby increasing BP. As shown in our preliminary data, sodium bicarbonate did not result in increased BP.⁴⁹ Sodium bicarbonate also has the potential for causing metabolic alkalosis and hypokalemia if it is retained rather than excreted in the urine. These expected adverse events will be monitored during the course of the study and in general, can be medically managed by

adjusting antihypertensive and/or diuretic agents, providing potassium replacement and by dietary changes. Of note, none of these adverse events were observed in our previous short-term pilot study. Patients will have safety visits and check-in calls to assess side effects and check laboratory values.

• Dose reduction and discontinuation:

- Serum bicarbonate >28 mEq/L: The intervention dose (study drug) will be reduced by 50% and diuretics will be adjusted as appropriate. The participant will return for a visit one week later to have serum chemistries rechecked. If the bicarbonate remains >28 mEq/L the intervention will be stopped and the participant will have serum bicarbonate measured weekly until it is <28 mEq/L. PI will monitor for symptoms of hypocalcemia as an increase in pH can decrease the ionized calcium concentration.^{117,118} Management of low calcium will be at the discretion of the PI based on symptoms reported by the patient.
- Systolic blood pressure ≥ 160 mmHg or diastolic blood pressure ≥ 90 mmHg: Potential reasons for uncontrolled BP, such as poor compliance or running out of medications will be evaluated and managed appropriately. If an identifiable cause is not found, the PI will increase anti-hypertensive medications and/or diuretics. The participant will return 1 week later for follow-up. If BP remains >160/90 mmHg at the second visit, medications will again be increased and the intervention dose will be reduced by 50%. The participant will return 1 week later. If BP remains unchanged at the third visit, the intervention will be stopped and medications will again be escalated. Participants will continue to have PRN visits weekly until BP is <160/90 mmHg.

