- Serum potassium < 3.0 mEq/L: The intervention dose will be reduced by 50%, diuretics will be adjusted as appropriate and potassium replacement will be prescribed. The participant will return 1 week later for repeat labs. If serum potassium remains < 3.0 mEq/L, the intervention will be discontinued. The participant will return weekly until serum potassium is > 3.0 mEq/L.
- Severe edema: If in the opinion of the PI severe edema (4+) is present and another etiology cannot be identified the dose of the intervention will be reduced by 50% and diuretics will be adjusted. If fluid retention remains severe at follow-up visits, the intervention will be discontinued.
- Rescue therapy with oral sodium bicarbonate: Rescue therapy with open-label sodium bicarbonate will be initiated if serum bicarbonate is <16 mEq/L on 2 consecutive measurements at least 1 week apart since a level <16 mEq/L may be associated with adverse outcomes. In this instance, open-labeled sodium bicarbonate will be given to target serum bicarbonate of ≥ 16 mEq/L. Participants will not discontinue study medications if open-labeled sodium bicarbonate is prescribed.

c) Exit Criteria. The primary exit criteria will include:

- Completion of the study
- Failure to comply with the requirements of the study
- The development of side effects described above as determined by the PI, [name]
- Subjects will have the option of withdrawing from the study at any time for personal

reasons.

The number of subjects exiting the study and the reason for the exit will be carefully documented.

7. Outcome Measures

a) Primary Outcome

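### Non-compliance and PI-judged side effects are grounds for leaving the study, no outcome follow-up after exit is stated, and the regression needs a 12-month value, so the comparison may become one of completers

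*Combined protocol and SAP*

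**What the plan says.** **Exit.** Besides completion and personal withdrawal, section c) Exit Criteria lists "Failure to comply with the requirements of the study" and "The development of side effects described above as determined by the PI". Non-compliance is not defined; it could mean pill-taking, which is checked at the in-person follow-up visits, or missed visits. The commitment made about people who exit is this: "The number of subjects exiting the study and the reason for the exit will be carefully documented".

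**Stopping study drug.** Dose reduction and discontinuation is a separate set of rules for high bicarbonate, raised blood pressure, low potassium and severe edema. After a stop it mostly names safety contacts; for high bicarbonate, for example, "the intervention will be stopped and the participant will have serum bicarbonate measured weekly". It does not mention outcome assessments.

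**Schedule.** The Follow-up list and section 7 (Outcome Measures) place cognition at baseline, 6 and 12 months, and the Doppler measures at baseline and 12 months. The schedule is not restricted to people still on drug.

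**Analysis.** Section 8 (Power and Statistical Analysis) regresses the end-of-study value on treatment, the baseline value, sex, age and baseline eGFR. It names no analysis set and no method for missing values, and it does not use the 6-month score.

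**The concern.** The side effects to which the exit list points back are those the protocol itself attributes to sodium bicarbonate: alkalosis, low potassium, edema and raised blood pressure, along with gastrointestinal complaints. Exit may therefore be more frequent in one arm. A participant who exits and is not assessed at month 12 has no response value and leaves the regression. If leaving is also related to cognition, what remains is a comparison of selected completers and not of the groups as randomised. Specific Aims says that the results will inform the design of a larger trial, so a completer estimate could be carried forward. A missed 12-month assessment cannot be recovered later.

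**Working it through.** **The plan's own figure.** A two-sided 0.05 two-sample t-test with 25 analysed per group and a standardised effect of 0.80 has noncentrality 0.80/√(2/25) = 2.83 on 48 df, and power 79.1%. The stated 79% is reproduced, but it is conditional on all 50 being analysed. With 25 and 20 analysed it would be 74.1%. Since the size was set by feasibility, the power figure is not the issue here.

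**Inputs for the bias (all assumed).**
- p: share lost, in the bicarbonate arm only: 4% (1 of 25), 8%, 12% or 20%
- ρ: correlation between the tendency to exit and the score it depends on: 0.3 to 0.5
- r: correlation between visits: 0.6 to 0.8
- no true treatment effect

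**Formulas, in SD units.** Completers are shifted by m = ρ·φ(z_p)/(1−p) on the score that drives exit.
- Exit depends on the 12-month outcome: the outcome shifts by m and baseline by r·m. Adjusting for baseline with slope r leaves m(1−r²).
- Exit depends on the 6-month score: the outcome and baseline both shift by r·m, leaving m·r(1−r).

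**Worked case, p = 0.20.** φ(z_p) = 0.280, and 0.280/0.80 = 0.350.
- ρ = 0.3, r = 0.8: m = 0.105, and 0.105 × 0.36 = 0.038.
- ρ = 0.5, r = 0.6: m = 0.175, and 0.175 × 0.64 = 0.112.

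| Loss, one arm only | Exit tied to 12-month outcome | Exit tied to 6-month score |
|---|---|---|
| 4% | 0.010–0.029 | 0.004–0.011 |
| 8% | 0.017–0.052 | 0.008–0.019 |
| 12% | 0.025–0.073 | 0.011–0.027 |
| 20% | 0.038–0.112 | 0.017–0.042 |

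With 20% loss in one arm and 8% in the other, and exit tied to the 12-month outcome, the factor is 0.350 − 0.162 = 0.188. This gives 0.3 × 0.188 × 0.36 = 0.020 up to 0.5 × 0.188 × 0.64 = 0.060. Simulated equal loss of 12% or 20% in both arms gave bias within 0.004 of zero.

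**Scale.** The adjusted standard error at 25 per arm is √(2/25)·√(1−r²): 0.283 × 0.80 = 0.226 at r = 0.6, and 0.283 × 0.60 = 0.170 at r = 0.8. The two ends of the 20% range are then 0.112/0.226 = 0.49 and 0.038/0.170 = 0.22 of a standard error. In the first, the two-sided type I error would be about 8% instead of 5% (normal approximation).

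**What retained follow-up does (20%, 12-month case).** If a share q of leavers is still assessed at month 12, m becomes ρ·φ(z_p)(1−q)/[1−p(1−q)].
- q = 0.5: 0.140/0.90 = 0.156, bias 0.017–0.050
- q = 0.8: 0.056/0.96 = 0.058, bias 0.006–0.019
- q = 1: 0

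A simulation with 1,000,000 per arm agreed with these and with the no-follow-up case to within 0.003.

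**What the 6-month score alone does (20% loss, simulated).** It leaves 0.03–0.10 where exit depends on the 12-month outcome, and about 0 where exit depends on the 6-month score.

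**The case against.** **Size.** The largest figure needs 20% loss in one arm and none in the other, exit tied to the unseen 12-month outcome, the higher exit correlation and the lower visit correlation, all together. The trial is a pilot sized on feasibility and not treated as confirmatory. This stands, and it limits the weight of the point.

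**Features that limit loss.** People judged unlikely to adhere, and those expecting dialysis or transplantation within 12 months, are excluded. Capsules are capped at six a day. The dose is reduced before any stop. Exit decisions are blinded, which does not prevent drug-related exit. The earlier crossover study reports that "Bicarbonate therapy was well tolerated and there were no significant adverse events", and the trial cited for the titration dose was "well tolerated without any significant differences in adverse events or hospitalization compared with placebo". This makes heavy one-sided loss less plausible. It does not exclude it: the sponsor's own experience is described as "none of these adverse events were observed in our previous short-term pilot study", and this trial lasts 12 months.

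**Drug stop is not exit.** A reader might infer that everyone whose drug is stopped is lost to outcome assessment. The documents do not support that. The two sets of rules are separate, and the visit schedule is not limited to people on drug. The remaining difficulty is that "The development of side effects described above as determined by the PI" refers back to the same events, so one event can be read as a drug stop with the person still in the study, or as an exit.

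**It may be handled elsewhere.** For the rationale behind eligibility the protocol says "please see the Recruitment and Retention Plan", and it refers to a protection of human subjects section for safety monitoring. Neither is supplied, and section 8 calls its own account brief. So it cannot be said that no follow-up provision exists. DSMB review of attrition is described, but that monitors loss and collects no outcomes.

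**Conclusion.** The point holds for people who exit for non-compliance or PI-judged side effects. The supplied text ends their participation without saying that outcomes are still sought, and the analysis has no place for anyone without a 12-month value. For people who only stop study drug it is an ambiguity to resolve. Severity is minor to moderate.

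The bias is probably small: about 0.01–0.05 SD at 4–8% one-arm loss and 0.04–0.11 SD at 20%, at most about half a standard error, and near zero if loss is balanced and alike in both arms or unrelated to outcome. Every loss rate and correlation behind these figures is assumed. A reader might infer that the trial will be materially biased towards bicarbonate; the documents support neither the size nor the direction, since they give no loss rate and do not show who would leave.

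**What to change.** 1. Reconcile the exit list with the intervention-stopping text, and say what counts as non-compliance. All drug-stopping rules stay with the sponsor.
2. State that non-compliance or stopping study drug does not end outcome follow-up, and that the scheduled 6- and 12-month assessments are sought from everyone randomised unless consent is withdrawn.
3. State that participants are analysed in their assigned group.
4. Optional, for outcomes measured at 6 months: use that score when month 12 is missing. One way is a mixed model with the 6- and 12-month values as responses, treatment, visit and their interaction, the planned covariates, and the 12-month contrast primary. This helps only where loss depends on observed scores, and adds nothing for anyone leaving before month 6. Keep the planned regression for the Doppler outcomes, which have no 6-month value.
5. If the Recruitment and Retention Plan or the human subjects section already covers items 1–3, a cross-reference is enough.

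**Cost.** Mostly wording. The assessments are already scheduled, so the extra work is seeing people who have left study drug. The downside is that off-drug follow-up may dilute an on-drug effect. In the worst case, where those leaving the bicarbonate arm keep no benefit, an effect of 0.80 becomes 0.80 × 0.92 = 0.74 at 8% leaving and 0.80 × 0.80 = 0.64 at 20%. Which effect to target is the sponsor's choice, but the plan should say so.

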In CKD, the ability of the kidney to excrete the daily dietary acid load progressively declines and patients develop a positive acid balance. The prevalence of metabolic acidosis increases as kidney function declines and is a common complication in patients with moderate CKD. Metabolic acidosis is associated with many complications in CKD including all-cause and cardiovascular mortality, kidney disease progression and vascular dysfunction. Metabolic acidosis results in inflammation and oxidative stress, both of which are associated with vascular endothelial dysfunction, arterial stiffness and decline in cognitive function. Central artery stiffening reduces cerebral blood flow impairing cerebrovascular function. Patients with cognitive impairment have lower mean cerebral blood flow compared to patients with normal cognition.

In our preliminary data, we show that treatment of metabolic acidosis with alkali therapy improves peripheral vascular dysfunction and we demonstrate that metabolic acidosis is associated with cognitive impairment in 2853 older hypertensive participants with and without CKD. Alkali therapy replacement may represent an inexpensive and novel therapeutic option for cognitive impairment in CKD. However, no interventional trials have been performed examining the effect of alkali therapy on cognitive function in older CKD patients.

Our primary goal of the present proposal is to perform a pilot study to determine the effect of alkali therapy on cognitive function in older adults (age 50-80 years) with CKD stage 3b-4 and metabolic acidosis (defined as serum bicarbonate level 16-22 mEq/L). Secondary goals are to determine the effect of alkali therapy on cerebrovascular dysfunction and established mediators of urinary acidification. We will conduct a pilot, prospective, randomized, double-blind clinical trial comparing the effect of oral sodium bicarbonate therapy vs. placebo in 50 CKD stage 3b-4 patients with metabolic acidosis to test the following aims:

Hypothesis 1: Treatment with sodium bicarbonate therapy vs. placebo will improve cognitive function in midlife and older adults with CKD stage 3b-4.

Specific Aim 1: To determine domains of cognitive function using the NIH Toolbox Cognitive Battery test and the Trail Making Test before and after 12 months of sodium bicarbonate therapy or placebo.

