- Cognitive Function: Cognitive function will be assessed using the NIH Toolbox-Cognition Battery computerized tests⁶² at baseline, 6 months, and 12 months. The NIH Toolbox-Cognition Battery entails seven computerized tests that assess five major cognitive subdomains including: 1) attention, 2) episodic memory, 3) working memory, 4) language, 5) executive function, and 6) processing speed. Administering the NIH Toolbox cognitive battery will yield the following summary scores, in addition to individual measure scores: Cognitive Function Composite Score ('g' factor, or general cognitive ability based on performance of each subdomain), Fluid Cognition Composite Score (includes tests of attention, executive function, working memory, and processing speed) and Crystallized Cognition Composite Score (includes Picture Vocabulary and Reading Recognition measures). These instruments have been validated in 476 participants ranging in age from 3 to 85 years, with representation from both sexes, 3 racial/ethnic categories and 3 levels of education.⁶² In addition, the Trail Making Test (TMT) parts A and B will be administered to determine processing speed and executive function, respectively.⁶³ The investigative team has experience administering these assessments.⁶⁴
- Justification for primary outcome: Our preliminary data suggests that correction of acidosis may improve cerebrovascular function. The use of the NIH Toolbox and the TMT parts A and B allow for assessing cognitive function in approximately 30-45 minutes and has been validated in numerous patient populations. Our research group has experience with these cognitive function measurements.⁶⁴

b) Secondary Outcomes

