8. Power and Statistical Analysis: Briefly, in this pilot study a total of 50 patients will be enrolled and equally randomized to the two groups. The two-sample t-test is applicable to compare the change between the two groups for each cognitive function subdomain and is the basis for power analysis. This sample size was determined based on feasibility and availability, not a specified statistical power. With a two-sided type I error rate of 0.05, the study will have a power of 79% to detect an effect of 0.80 if 25 patients per group can be included in the final analysis. This power calculation applies to the secondary and other outcome variables. For Aim 1, we will assess the treatment effect on each of the six subdomains of cognitive function by a linear regression model with the measure at end of study regressed on treatment along with the baseline measure of the subdomain, sex, age, and baseline eGFR. Conclusion will be subdomain specific. For Aims 2 and 3, the linear regression model will be used to examine the treatment effect on the secondary and other outcomes. Particularly, the measure of an outcome variable at end of study will be regressed on intervention indicator and baseline measure of the outcome variable plus sex, age and baseline eGFR for adjustment purpose.

9. Potential Problems and Alternative Strategies

- Although subject recruitment and retention are always challenging, we should be able to complete the study in the proposed timeline given our groups excellent track record in recruiting participants in clinical trials.
- We should have few difficulties with the proposed experimental procedures and protocols as they are already established in the vascular laboratories at the KDRC by [name].
- We recognize that alternative approaches exist for examining the effects of alkali therapy on cognitive function in patients with CKD. For example, one alternative would be to undertake a larger study to examine structural changes with brain MRIs rather than the investigation proposed in the current application. However, our proposed study is the most cost-effective approach to obtain confirmation of the study hypotheses.

- We recognize that different dosages of sodium bicarbonate therapy can be used. However, the proposed dose in the current study has been shown to be safe and effective in treating metabolic acidosis in CKD 3-4.

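### Does Hypothesis 1 need a composite endpoint or a multiplicity adjustment because Aim 1 is analysed as six separate subdomain tests?

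*Combined protocol and SAP*

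**What the plan says.** Section I states Hypothesis 1 globally: "Treatment with sodium bicarbonate therapy vs. placebo will improve cognitive function in midlife and older adults with CKD stage 3b-4". The aim paired with it is narrower: "To determine domains of cognitive function using the NIH Toolbox Cognitive Battery test and the Trail Making Test", before and after 12 months of treatment.

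Section IV.7 a) makes the NIH Toolbox cognition battery, with Trail Making parts A and B, the primary outcome. It lists three summary scores that the battery yields. The overall one is described as "general cognitive ability based on performance of each subdomain". None is named as the primary variable.

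Section IV.8 works at subdomain level throughout. The power basis is "The two-sample t-test is applicable to compare the change between the two groups for each cognitive function subdomain". For Aim 1, "we will assess the treatment effect on each of the six subdomains of cognitive function" by a regression of the end-of-study value on treatment, baseline value, sex, age and baseline eGFR. The rule for inference is short: "Conclusion will be subdomain specific". On size it says "This sample size was determined based on feasibility and availability, not a specified statistical power". Section I calls the trial a pilot that will inform a larger one, and the Data Safety Monitoring Board paragraph stops short of calling it confirmatory.

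**The concern.** One broad hypothesis faces six tests, each at 0.05. The documents contain no composite model, hierarchy, global test or adjustment, and no sentence says what pattern of results would support Hypothesis 1. The overall composite, whose description fits the hypothesis best, is collected but does not appear in the analysis section. Section IV.9 also describes the trial in stronger terms: "our proposed study is the most cost-effective approach to obtain confirmation of the study hypotheses".

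The risk is that one positive subdomain out of six is reported as improved cognition in general and carried into the design of the larger trial. Under that reading the nominal 5% would understate the chance of a false claim several times over.

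**Working it through.** **1. The plan's own figure.** Inputs from IV.8: 25 per group, effect 0.80 (read as a standardised difference, since no SD is given), two-sided 0.05. Noncentrality = 0.80 × √(25/2) = 2.83 on 48 degrees of freedom. Power from the noncentral t distribution = 79.1%, which matches the stated 79%. It is the power of one subdomain test at an unadjusted 0.05, and that is what IV.8 presents it as.

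**2. Chance of at least one significant result among six when nothing works.** For independent subdomains:

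- either direction: 1 − 0.95⁶ = 26.5%
- direction of benefit only: 1 − 0.975⁶ = 14.1%

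The documents give no correlations between subdomains, so common values of 0.5 and 0.7 are assumed. Simulation of six two-sample t-tests (200,000 trials per value) gives:

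| Assumed r | Any significant | Any false improvement |
|---|---|---|
| 0 | 26.5% | 14.1% |
| 0.5 | 21.0% | 10.5% |
| 0.7 | 16.6% | 8.2% |

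The planned covariate-adjusted regression (20,000 trials per value, assumed baseline-to-end correlation 0.7) gives 26.8%, 20.7% and 16.5% for any significant result, so the choice of model does not matter here.

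**3. What these rates measure.** They are the probability that at least one of six tests is significant. They become an error rate for Hypothesis 1 only if one success among six counts as support for it. Under the rule in IV.8, each claim concerns one subdomain and carries its own error: 5% two-sided, 2.5% for a false improvement.

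**4. What a formal repair would cost.** Take a composite of six equally weighted, equally correlated components (an assumption), j of which carry the effect 0.80. The sum has mean difference j × 0.80 and variance 6 + 30r, so the composite effect is j × 0.80/√(6 + 30r). For j = 2, with Holm adjustment across the six for comparison:

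| Assumed r | Composite effect | Composite power | Holm finds at least one of the two |
|---|---|---|---|
| 0 | 1.6/√6 = 0.653 | 61.9% | 78.4% |
| 0.5 | 1.6/√21 = 0.349 | 22.7% | 70.5% |
| 0.7 | 1.6/√27 = 0.308 | 18.7% | 66.6% |

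If all six domains respond, the order reverses. At r = 0.5 the composite effect is 4.8/√21 = 1.05, with 95.2% power against 88.5% for Holm. The two columns support different claims, a global effect and an effect in at least one domain, so neither method is simply better.

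At the strictest adjusted level, 0.05/6 = 0.0083, power for one subdomain is 53.5%. Keeping 79% there would need 39 per arm, 78 in total, against the 50 planned.

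**The case for a change.** The best case for a change is that a rule for Hypothesis 1 controls error only if it is fixed before unblinding, and that fixing it costs a sentence or two. Aim 1 is nowhere labelled exploratory, and the statement that conclusions are by subdomain does not expressly forbid citing one of them for the broader hypothesis. The composites exist already and would need no new data.

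Part of this stands. No sentence links the six results to Hypothesis 1, and IV.8 models none of the composites listed in IV.7. Nor does it name Trail Making A and B. Counting those two makes eight tests, with a chance of at least one false positive of 1 − 0.95⁸ = 33.7% if independent. Section IV.7 also announces five subdomains and then lists six, a clerical slip that the count of six in IV.8 settles.

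The rest is weaker. The phrase about confirmation in IV.9 comes from a comparison of cost with a larger brain-MRI study and sets no decision rule. A sentence saying that one subdomain result does not establish the global hypothesis would largely restate IV.8, and it would alter no estimate, interval or p-value. A composite or Holm test would go further, but which one helps depends on how many domains respond and how they correlate, and the documents inform neither.

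**Conclusion.** No change follows. Carried out as written, the plan gives six subdomain conclusions, each with a valid 5% error rate, which suits a feasibility-sized pilot meant to guide a larger trial. The any-of-six rates (26.5% if independent, about 21% and 16 to 17% at assumed correlations of 0.5 and 0.7) belong to a one-success-is-enough rule that the plan does not adopt and that its statement on conclusions argues against.

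What remains is a wording gap between a broad hypothesis and a narrower aim, which an analyst following IV.8 fills by reporting each result for its own subdomain. A formal global test is a fair trade-off for the sponsor, not a correction: a composite ranges from about 19% power (two domains affected, r = 0.7) to about 95% (all six, r = 0.5). These figures assume equal weights, a common correlation, a standardised effect of 0.80 and 25 analysed per arm.
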